Document Cover Page

Official Title of the Study: Improving Parent-Child Interactions to Enhance Child Health

NCT Number: NCT03982511

Date of Document: 4/5/2023

Study Protocol and Statistical Analysis Plan (SAP)

Study Protocol

After determining eligibility, potential participants will be invited to the Center for Children, Families, and Communities (CCFC) to provide consent and complete baseline measures. Following completion of clinic-based baseline measures, participants will be instructed on how to complete home-based baseline measures (e.g., family mealtime recordings, Actigraphs). One week later, research assistants will obtain home-based assessments from families' homes. After these assessments are completed, research assistants will inform families whether they have been randomly assigned to intervention or waitlist control condition. Random assignment will be determined by random number generator and stratified by child sex. See Table 1 for assessment protocol and timeline. Participants in the intervention condition will receive PCIT-Health and participants in the waitlist control condition will be offered the intervention after 6-month post-intervention measures are completed (i.e., 10 months after they have enrolled in the study). After baseline, assessments will occur: (1) at completion of PCIT-Health intervention and (2) at 6-months post-intervention completion. All participants (regardless of condition) will complete these additional assessments after baseline. In other words, all participants will complete three different assessments.

PCIT-Health Intervention

Given that the pandemic necessitated virtual delivery of treatment, a telehealth version of PCIT-Health was delivered. See Domoff et al. (2022) for how PCIT-Health (Domoff & Niec, 2018) was adapted to be delivered through virtual conferencing. PCIT-Health consists of three phases: Child-Directed Interaction (CDI), Parent-Directed Interaction (PDI), and Health-Directed Interaction (HDI; Domoff & Niec, 2018). During CDI, parents learn child-centered play/interaction skills to enhance the parent-child relationship. During PDI, parents learn age/developmentally- appropriate discipline skills. In the HDI teaching session, we provide psycho-education about beneficial parenting practices in areas specific to children's weight-related behaviors: parental feeding practices and parenting around screen time (i.e., media parenting). Three coaching sessions (guided and reinforced implementation of skills learned in the teaching session) focus on two primary contexts where children are socialized around eating and activity: (1) family mealtime and (2) unstructured child play/free time (see Domoff et al., 2022 & Domoff & Niec, 2018 for more comprehensive descriptions of the sessions).

References:

Domoff, S. E., & Niec, L. N. (2018). Parent-child interaction therapy as a prevention model for childhood obesity: A novel application for high-risk families. *Children and Youth Services Review*, 91, 77-84.

Domoff, S. E., Overton, M. M., Borgen, A. L., & Niec, L. N. (2022). Adapting PCIT-Health for Telehealth Delivery: A Case Study. *International Journal of Environmental Research and Public Health*, 19(14), 8352.

Measures

Feasibility and Acceptability Measures (AIM 1)

Feasibility and acceptability measures will be administered once, at treatment completion. The acceptability of PCIT-Health will be measured by the Abbreviated Acceptability Rating Profile (AARP) and Therapy Attitude Inventory (TAI), which assesses parents' satisfaction with parent training interventions. Both measures have strong psychometric properties. The Barriers to Treatment Participation Scale (BTPS) will be administered as well.

Primary (AIM 2) and Secondary (AIM 3) Outcome Measures

The following measures will be assessed at each time point (baseline, post-treatment, and 6-month follow-up). There has been increasing recognition of need for observational measures of parenting; as such, we will assess secondary outcomes of PCIT-Health (e.g., parent-child relationship quality, and parent behavior management skills in general and obesity-specific contexts) using both observational and parent-report measures (see below and Table 1 for assessment visit activities).

Child Anthropometrics

Change of child BMI z-score from baseline to (1) completion of PCIT-Health and (2) six-month follow-up will be calculated as the primary outcome variable (**AIM 2**). Child height and weight will be measured by trained research assistants, using a Detecto Portable Scale Model and a Seca portable stadiometer. Children will be weighed twice and if the two readings differed by more than 0.1 kg, the child will be weighed two more times. For the height measurement, the child's position and posture will be checked, and height will also be measured twice. As with weight, if measurements differ by more than 0.5 cm, two more measurements will be taken. BMI will be calculated and the child BMI z-score will be derived using age- and sex-specific norms.

Child Self-Regulation

Emotion Regulation Checklist (ERC) is a 24-item parent-report measure that assesses parents' perception of their child's affective regulation and emotionality. Two subscales are calculated based on parent responses. The first, Emotion Regulation,

Table 1. Protocol	
Time	Activity
Clinic Assessments	
4pm	Instructions for Clinic Visit
4:15	Parent completes questionnaires
5:15	DPICS protocol
5:45	Child and caregiver anthropometry
5:55	Instructions for home based measures
Home Assessments	
Frequency/Description	
3 dinners	Family Mealtime Recordings
7 days	Actigraph assessments

assesses a child's adaptive regulation and expression or emotion. The second, Lability/Negativity, assesses a child's emotional intensity, negative reactivity, and dysregulation of positive emotions.

Child Weight-Related Behaviors

Child Screen Time. Caregivers will report on children's typical weekday and weekend screen time (including TV, tablet, computer, video game use). Items request caregivers to give estimates based on different parts of the day (e.g., "How many hours did your child [watch TV/videos/use mobile device/use computer/play video games] from the time he/she wakes up until going to [daycare/preschool]" to facilitate recall. Parents will also report on Problematic Media Use (Domoff et al.,2019).

Child Physical Activity. Objective measures of habitual physical activity will be monitored by a wGT3X-BT Actigraph accelerometer (ActiGraph of Ft. Pensacola, FL) and analysis with ActiLife6 software (ActiGraph of Ft. Pensacola, FL). Participants will be asked to wear the device for seven consecutive days while they are awake and to remove it while swimming or bathing. Any block of time greater than or equal to 60 minutes where the activity count is equal to zero will be considered time when the monitor was not worn. Each minute of accelerometer data will be coded based on the recorded activity counts for that minute associated with sedentary, moderate, moderate-to-vigorous, and vigorous physical activity as previously described in children.

Parent-Child Relationship Quality

Dyadic Parent-Child Interaction Coding System-IV (DPICS-IV). The DPICS is a standardized, behavior observation measure of parent-child interactions during three situations in which parents must exert increasing control over their children. It provides a reliable measure of parenting behaviors (e.g., child-centered skills, positive and negative physical interaction, use of contingent reinforcement).

Parenting Stress Index, Fourth Edition, Short Form (PSI-4/SF). The PSI-4/SF is a 36-item self-report measure assessing parenting distress in parents of children 3 months to 12 years of age. Three subscales are included: Parental Distress assesses distress related to a respondent's role as a parent; Parent-child Dysfunctional Interaction assesses distress associated with a parent's relationship with a target child; Difficult Child (DC) assesses distress associated with a target child's difficult behaviors. The PSI has demonstrated good to excellent reliability and validity, including internal consistency, test-retest reliability, and discriminant and factorial validity. Scores on the Parent-child Dysfunctional Interaction subscale will be used as the parent-report of parent-child relationship quality.

Parent Behavior Management Skills in General and Obesity-Specific Contexts

Parent behavior management skills in general (non-obesity specific contexts) will be measured by the DPICS-IV. Parent behavior management skills in obesity-specific contexts will be measured in the domains of feeding and screen media use. Parents will

complete self-report measures (detailed below) and research assistants will code recordings of family mealtime observations to assess behavior management skills in the obesity-specific context.

Parent feeding practices and styles. How caregivers feed their children will be measured by parent report on the subscales of Pressure to Eat and Restriction on the Child Feeding Questionnaire (CFQ) and Caregivers' Feeding Styles Questionnaire, Emotional feeding (using food to help regulate child's emotions) and instrumental feeding (using food as a reward) will be measured with respective subscales on the Parental Feeding Style Questionnaire.

Media parenting practices. Parenting practices related to children's media exposure and screen time will be measured by self-report, using the Parental Mediation Scale. This Scale measures three types of media parenting: active mediation, co-viewing, and restrictive mediation and has strong psychometric properties. Caregivers will also report on other aspects of media parenting practices related to child obesity risk, including the number of screens in the home and in the child's bedroom.

Observational Coding of Parenting during Mealtime. Family mealtime characteristics and interactions will be assessed through coding of recorded family mealtimes. Caregivers will be provided a videorecorder and tripod and instructed how to record three typical dinnertime meals in the home. These video recordings will be coded for a variety of behaviors. **Parent feeding behaviors** will be coded using an adapted version of the Mealtime Interaction Coding System. **Media parenting practices** (e.g., presence of screen media, type(s) of screen media present, TV on) during mealtime will be coded.

Statistical Analysis Plan

Aim 1. To assess the acceptability and feasibility of the PCIT-Health intervention delivery and assessment methods.

To address Aim 1, descriptive statistics (e.g., means and frequencies) of the parent-report measures assessing acceptability of PCIT-Health (e.g., AARP, TAI, and BTPS) will be calculated. Proportions of treatment completers to enrollees will be calculated as well as frequencies of total sessions attended. In addition we will use multivariate regression models to identify factors that increase/decrease PCIT-health participation. Such information would be valuable and will be used to enhance participation in the program.

Aim 2. To test the preliminary efficacy and estimate the effect size of PCIT-Health in parent-child dyads randomly assigned to PCIT-Health or wait-list control on change in child BMI z-score (primary outcome) from baseline to (1) treatment completion and (2) 6-month post-intervention follow-up.

Repeated measure ANOVA will be used for testing change in child BMI z-scores between (1) baseline and post-intervention and (2) baseline and 6 month follow up will

be conducted. Given that the sample size is not very large for this study, we will report both statistical significance as well as the effect size. The magnitude of the effect size would show the potential effect of PCIT-Health when applied to a larger population.

Aim 3. To explore the effect of PCIT-Health on the following secondary outcomes: (1) child self-regulation, (2) child eating behaviors, (3) physical activity, and (4) child screen media use.

Similar to Aim 2, repeated measure ANOVA will be used for testing change in secondary outcomes between (1) baseline and post-intervention and (2) baseline and 6 month follow up will be conducted. Both the significance level and the effect size will be reported to fully understand the magnitude of the treatment effect.

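### Aim 1 includes the assessment methods, but no Aim 1 measure or analysis covers them, and it is not stated whether families who stop early answer the Aim 1 scales

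*Combined protocol and SAP*

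**What the plan says.** The SAP gives Aim 1 as "To assess the acceptability and feasibility of the PCIT-Health intervention delivery and assessment methods". The aim thus has two objects, the intervention delivery and the assessment methods, and two properties to be judged for each, acceptability and feasibility.

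The protocol section on Feasibility and Acceptability Measures (AIM 1) names three parent-report scales (AARP, TAI, BTPS) and says: "Feasibility and acceptability measures will be administered once, at treatment completion". The SAP text under Aim 1 then lists descriptive statistics of those scales, the proportion of enrollees who complete treatment, the number of sessions attended, and regression models for factors linked to participation in PCIT-Health.

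On who is seen and when, the Study Protocol section says of both arms: "In other words, all participants will complete three different assessments". Wait-list families "will be offered the intervention after 6-month post-intervention measures are completed (i.e., 10 months after they have enrolled in the study"). The outcome measures follow a fixed schedule: "The following measures will be assessed at each time point (baseline, post-treatment, and 6-month follow-up").

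**The concern.** If the plan is followed as written, one of the two objects of Aim 1 is never reported on. The efficacy aim is described as preliminary, so feasibility is a main product of this trial. A later trial would need to know whether families can manage the home recordings and the accelerometer.

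The scales raise a related question. The BTPS asks about barriers to taking part, and the plan intends to use what Aim 1 shows to raise participation. If only families who finish treatment answer, the barrier ratings of those who stopped are missing.

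**Working it through.** There is no stated figure to reproduce: the documents give no sample size, allocation ratio or feasibility target. The check sets the aim against what is planned for it.

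**1. Coverage of the aim**

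| Object of Aim 1 | Measures named for Aim 1 | Analyses named for Aim 1 |
|---|---|---|
| Intervention delivery | AARP, TAI, BTPS | Scale descriptives, completion proportion, sessions attended, regression on participation |
| Assessment methods | None | None |

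The scale list in the SAP is introduced as examples, but of measures of the acceptability of PCIT-Health, so it does not extend to the assessments.

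**2. Are data for the second row already planned?**

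For feasibility, yes. There are 3 time points (Primary and Secondary Outcome Measures), 3 dinners each time (Observational Coding of Parenting during Mealtime) and 7 accelerometer days each time (Child Physical Activity).

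- Dinner recordings per family: 3 × 3 = 9.
- Accelerometer days per family: 3 × 7 = 21.

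These are the planned load and the natural denominators. They do not measure bias or loss.

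The accelerometer rule treats a run of zero counts lasting 60 minutes or more as non-wear. It yields wear time per day but does not define a worn day. The device is worn only while awake and comes off for bathing and swimming, so some non-wear is expected every day. A count of worn days therefore needs a minimum wear time, which the documents do not give.

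For acceptability, no. No planned instrument asks families about the assessments.

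**3. Which families answer the scales?**

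- *Literal reading.* The scales are given when a family completes treatment, so families who stop early do not answer.
- *Time-point reading.* The Study Protocol section uses completion of PCIT-Health as the label of the first follow-up for both arms, including wait-list families not yet treated. Families who stop early would then answer at that visit.

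The documents do not choose, and they name no arm for the scales. The wait-list timing adds to this. The post-treatment time point falls at about 10 − 6 = 4 months. If wait-list treatment takes as long (an assumption), it ends at about 10 + 4 = 14 months, after the last planned assessment at about month 10.

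**4. The completion proportion (illustration only)**

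Let *s* be the share of families assigned to PCIT-Health and *c* the completion rate among them. If all randomised families were the denominator and no wait-list family had yet been treated, the proportion would be *s* × *c*, with ceiling *s*.

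- Assumed 1:1 allocation: ceiling 50%; with an assumed *c* of 80%, 0.5 × 0.8 = 40%.
- Assumed 2:1 allocation: ceiling 67%; with the same *c*, 0.667 × 0.8 = 53%.

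With families randomised to PCIT-Health as the denominator, the same data give 80%.

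**The case against.** Four counter-arguments deserve weight.

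- *The time-point reading of completion is reasonable.* This stands. A reader might infer that the ratings will come from completers only, but the documents do not establish that; they leave it open.
- *Information on early leavers would not be wholly lost.* This also stands. Nothing in the SAP restricts the session counts or the participation regression to completers. On the literal reading, what is lost is the early leavers' scale ratings, including the BTPS.
- *The natural sense of enrollees is families enrolled in treatment*, since the proportion shares a sentence with sessions attended. This largely stands. The protocol does speak of wait-list families as having enrolled in the study, so a definition is useful. However, a reader might infer that the plan will understate completion, and the documents do not support that. The 50%, 67%, 40% and 53% figures need an assumed allocation, an assumed completion rate and an analyst who counts families not yet offered treatment.
- *Counting dinners and wear would not answer the whole aim.* This is correct. Counts speak to feasibility; the acceptability of the assessments would still have no measure.

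None of these removes the main gap: the assessment methods are named in the aim and appear nowhere in its measures or analysis.

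**Conclusion.** The concern holds for two matters. First, one of the two objects of Aim 1 has neither a measure nor an analysis. This rests on the text alone and needs no assumption. Its feasibility part can be answered from planned data; its acceptability part cannot. Second, it is not stated whether families who stop early answer AARP, TAI and BTPS, and the literal reading would exclude them.

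The meaning of enrollees is a clarification only, because analysts would probably settle it sensibly; the percentages shown illustrate a possible misreading, not an error in the plan. No bias in the scale scores is quantified, as the documents give no basis for it. None of this affects the analysis of BMI z-score.

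**What to change.** **Assessment methods.** Add to the Aim 1 analysis, by time point:

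- visit and questionnaire completion;
- dinners recorded out of 3;
- accelerometer wear over the 7 days, as hours per day from the existing non-wear rule and as days meeting a minimum wear time fixed before analysis.

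Give baseline figures over all consented families, because assignment is disclosed only after baseline: "After these assessments are completed, research assistants will inform families whether they have been randomly assigned". Give follow-up figures by randomised arm. Then either narrow the aim to feasibility of the assessment methods or add a short item on their acceptability.

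**Scales.** Tie AARP, TAI and BTPS to the post-treatment assessment for every family randomised to PCIT-Health, whatever their completion status. Report them overall and by completion status, with respondents out of those assigned.

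**Clarification.** State that enrollees in the completion proportion means families randomised to PCIT-Health, and report wait-list families treated later separately.

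**Cost.** A few sentences in the protocol and SAP. The feasibility counts and the denominator need no new data. Families who stop early would be asked for one questionnaire set, with a likely lower response, which the respondent counts would show. An acceptability item, if chosen, is a small addition. The protocol already says in the past tense that "a telehealth version of PCIT-Health was delivered", so scale collection may be over for some families. For them, label the results by who answered and give the respondent counts.

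### Aims 2 and 3 test change by repeated-measures ANOVA: valid, but a baseline- and sex-adjusted model would use the same data better, mainly for outcomes only modestly correlated with baseline

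*Combined protocol and SAP*

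**What the plan says.** The Aim 2 paragraph of the Statistical Analysis Plan gives the primary method: "Repeated measure ANOVA will be used for testing change in child BMI z-scores between (1) baseline and post-intervention", and likewise from baseline to the 6-month follow-up. Aim 3 carries the method over: "Similar to Aim 2, repeated measure ANOVA will be used for testing change in secondary outcomes". Neither paragraph names a baseline covariate, a sex term, an arm-by-visit contrast or a rule for missed visits. The Aim 2 heading does make clear that dyads are compared as randomised.

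Three other places bear on the choice:

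- Study Protocol section, on allocation: "Random assignment will be determined by random number generator and stratified by child sex".
- Study Protocol section, on visits: "After baseline, assessments will occur: (1) at completion of PCIT-Health intervention and (2) at 6-months post-intervention completion", and "All participants (regardless of condition) will complete these additional assessments after baseline".
- Child Anthropometrics: "BMI will be calculated and the child BMI z-score will be derived using age- and sex-specific norms".

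The SAP also concedes limited size: "Given that the sample size is not very large for this study, we will report both statistical significance as well as the effect size". It then presents the effect size as a guide to what the programme might achieve more widely.

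**The concern.** Because the plan treats the effect size as a guide to larger use, the estimate and its precision are the trial's main product. The named method leaves three improvements unused.

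1. **Baseline is subtracted, not conditioned on.** Subtraction assumes a slope of 1 on baseline. When the true slope is lower, the estimate is noisier than it need be, and a chance baseline imbalance is only partly corrected.
2. **The stratum is ignored in the analysis.** If sex predicts change, leaving it out makes the test slightly conservative.
3. **Missed visits.** Classical repeated-measures ANOVA by default excludes a child missing a visit it models. A post-intervention value then cannot inform the 6-month contrast for a child absent at month 6. If that absence differs by arm and relates to outcome, the 6-month estimate is biased. Nothing in the documents shows that this will happen, and stopping treatment is not the same as missing an assessment.

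**Working it through.** **Inputs.** The plan has no sample size, power or SD calculation to reproduce. Taken from the documents: two arms, three visits, stratification by sex, an outcome already sex-normed. Assumed: 1:1 allocation, two-sided 5% test, 15 to 30 per arm, baseline to follow-up correlation r from 0.4 to 0.95, equal SDs across visits unless stated, outcome in SD units.

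**Variance.** Per child, the change-score variance is 2(1 − r) and the large-sample ANCOVA variance is 1 − r². Their ratio is 2/(1 + r):

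| r | 0.4 | 0.5 | 0.7 | 0.8 | 0.9 | 0.95 |
|---|---|---|---|---|---|---|
| Ratio | 1.43 | 1.33 | 1.18 | 1.11 | 1.05 | 1.03 |

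With unequal SDs, and k = baseline SD / follow-up SD, the ratio is (k² + 1 − 2rk)/(1 − r²). At k = 0.8 it is 1.12 (r = 0.5) and 1.02 (r = 0.7); at k = 1.25 it is 1.75 and 1.59. It never falls below 1, because k² + 1 − 2rk − (1 − r²) = (k − r)² ≥ 0.

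**Power and precision.** Noncentral t, effect 0.5 SD, n per arm. Change score: 2n − 2 degrees of freedom. ANCOVA with baseline and sex: 2n − 4 degrees of freedom, variance inflated by 1 + 1/(2n − 4). Each cell is change score v ANCOVA.

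| r | Power, n = 15 | Power, n = 20 | Power, n = 30 | 95% CI half-width, n = 20 (SD) |
|---|---|---|---|---|
| 0.5 | 0.26 v 0.32 | 0.34 v 0.42 | 0.48 v 0.59 | 0.64 v 0.56 |
| 0.7 | 0.40 v 0.44 | 0.51 v 0.57 | 0.69 v 0.75 | 0.50 v 0.46 |
| 0.9 | 0.84 v 0.84 | 0.93 v 0.94 | 0.99 v 0.99 | 0.286 v 0.283 |
| 0.95 | – | – | – | 0.202 v 0.203 |

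A harsher charge for the two covariates, 1 + 2/(2n − 5), gives 0.287 at r = 0.9 and 0.206 at r = 0.95 with 20 per arm. Adjustment is then marginally worse than the change score. Under that charge, break-even r is about 0.77 at 10 per arm, 0.89 at 20 and 0.95 at 40.

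**Chance imbalance.** One standard error of the baseline difference at 20 per arm is √(2/20) = 0.32 SD. The change-score estimate shifts by (1 − r) × 0.32: 0.16, 0.10 and 0.03 SD at r = 0.5, 0.7 and 0.9.

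**Sex.** In simulation with 10 children per sex per arm, ignoring the balanced stratum gave type I error of 4.9%, 4.3% and 3.5% for sex effects of 0.2, 0.5 and 0.8 SD on change.

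**Missed visits.** If all three visits enter one ANOVA and 20% of children independently miss each follow-up, 0.8 × 0.8 = 64% remain. For bias, 6-month loss was simulated in the intervention arm only, driven by early change, with no true effect:

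- Mild case (10–20% loss, odds ratio 1.6 per SD): complete-case bias is −0.01 to −0.05 SD.
- Stress case (30% loss, odds ratio 7.4), bias in SD:

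| Correlation | Complete-case change | Mixed model, no dropout has a post-intervention value | Half do | All do |
|---|---|---|---|---|
| Exchangeable 0.9 | −0.08 | −0.08 | −0.03 | about 0 |
| Exchangeable 0.7 | −0.15 | −0.10 | −0.04 | about 0 |
| Exchangeable 0.5 | −0.19 | −0.10 | −0.04 | about 0 |
| Autoregressive 0.85 | −0.19 | −0.16 | −0.07 | about 0 |

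With no post-intervention value, the mixed model equals complete-case ANCOVA. Bias is about 0 if loss is random or follows the same mechanism in both arms.

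**The case against.** The planned test is valid and matches the declared primary outcome, which is change. On that outcome the proposed gain nearly vanishes: BMI z-score may well be highly correlated with its baseline, and it is already sex-normed. In a very small sample, adjustment could even cost a little precision. What remains is efficiency in Aim 3, which is exploratory and includes screen-time hours and accelerometer minutes that may be too skewed for normal-theory power figures. Every input is assumed, and the percentages move a good deal when SDs differ between visits. The attrition argument has no dropout rate behind it. The SAP can also be read as two separate two-visit analyses, so a child absent at month 6 would still count in the first. Silence on covariates is not exclusion.

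Most of this stands, and it limits the point to one of efficiency and specification. It does not remove it. The correlation is unknown for every outcome, and the adjusted model loses almost nothing at high r while gaining materially at modest r. Unequal SDs alter the size of the large-sample advantage but cannot reverse it. Change need not be abandoned: with baseline in the model, the arm difference is the same whether the response is change or the follow-up value. Under the two-analysis reading, the 6-month comparison still discards the post-intervention value of a child absent at month 6, and the plan still does not say how such a child is handled.

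**Conclusion.** The concern holds as a recommended improvement, not as an error of validity. If the arm-by-time contrast is the test and data are complete, the planned analysis is sound.

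- **Primary outcome:** at r of about 0.9 or above, the gain from adjustment is about 5% of variance or less, and nil or slightly negative with 20 or fewer per arm.
- **Aim 3 outcomes:** at r of 0.5 to 0.7 with equal SDs, the change score carries 18% to 33% more variance. At 20 per arm that is 5 to 8 percentage points of power for a 0.5 SD effect.
- **Sex:** omission makes the test at most slightly conservative.
- **Attrition bias:** only a possibility. In the mild case it is small against CI half-widths of 0.29 to 0.64 SD.

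The algebra is secure. The size of the benefit in this trial depends on sample size, correlation and missing-visit rates that the documents do not state.

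**What to change.** In Aims 2 and 3, specify a mixed model for repeated measures on the post-intervention and 6-month values. Fixed effects: arm, visit, arm × visit, baseline value of the outcome, baseline × visit and child sex. Use an unstructured covariance and Kenward-Roger degrees of freedom. ANCOVA with baseline and sex at each visit is an acceptable simpler choice, but it does not recover a child missing that visit.

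Report the adjusted between-arm difference with its 95% CI at each visit. Analyse by assigned arm, including every randomised child with at least one follow-up value. Report by arm the number with no follow-up value, and missed visits with reasons. State that the mixed model corrects outcome-related 6-month dropout mainly when the post-intervention value was observed; with both follow-ups missing it does no better than complete-case ANCOVA.

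The cost is SAP wording, routine code and one to three degrees of freedom, with no new data. At r near 0.95 and 15 per arm, the CI half-width becomes marginally wider: 0.237 SD for the change score, 0.239 SD adjusted. Timing needs care. The document is dated 4/5/2023 and the PCIT-Health Intervention section describes delivery in the past tense: "Given that the pandemic necessitated virtual delivery of treatment, a telehealth version of PCIT-Health was delivered". If outcomes have already been examined, date and label the change as made afterwards, and report the planned ANOVA alongside it.
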